Statistical Methods:	
Analysis:
 
All statistical analyses will be undertaken at study closure and will incorporate all Week 24 and Week 52 endpoints.
 
Populations:
 
The efficacy analysis will be based on the intent-to-treat (ITT) principles and will consist of all randomized subjects.
 
The per-protocol set will be a subset of subjects in the ITT population who do not have any major protocol violations (to be defined prior to unblinding).
 
The safety analysis set will consist of all subjects who receive at least 1 dose of study treatment.
 
Methods:
 
The primary analysis of the primary endpoint, renal response at Week 52, will be conducted on the ITT population. The relative renal response for Orelvo compared to placebo will be determined using logistic regression. The logistic regression model will include terms for treatment, baseline UPCR, biopsy class, and MMF use at baseline. Results of this logistic regression will be displayed as odds ratios and a 2-sided confidence interval (CI) (Orelvo compared to placebo). The proportion of subjects exhibiting renal response at Weeks 24 and 52 will be summarized by treatment group.
 
The analyses of the secondary endpoints are described below:
 
Other binary endpoints will be analyzed in a similar manner to the primary endpoint. Endpoints measured as a time-to-event will be displayed using Kaplan-Meier methodology. Orelvo will be compared to placebo using a Cox proportional hazard model. The model will include terms for treatment and appropriate baseline assessments. Median time-to-event along with 2-sided CIs will be displayed.
 
Other endpoints will be summarized by visit and differences between baseline and on-treatment values at weeks up to and including Week 52 will be analyzed using Mixed Effect Model Repeated Measures (MMRM). The MMRM model will include terms for treatment, visit, treatment by visit interaction and baseline. Results will be expressed as differences between treatment arms (along with associated 95% CI).
 
Safety Endpoints:
 
Adverse events will be aggregated by System Organ Class and preferred term and presented as summary tables.
 
Laboratory values (based on results from the central laboratory), vital signs and other safety parameters will be summarized by visit as absolute values and change from baseline. Laboratory values outside of defined normal ranges will be summarized.
 
The impact of withdrawals on primary endpoint will be investigated with a tipping point analysis.

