### **13.7.2 Secondary Endpoints**

#### **13.7.2.1 Key Secondary Endpoints**

- Time to UPCR of  $\leq 0.5$  mg/mg
- Partial renal response as defined by 50% reduction from baseline UPCR at Weeks 24 and 52
- Time to 50% reduction in UPCR from baseline
- Renal response at Week 52 (based on definition of primary endpoint)
- Duration of UPCR  $\leq 0.5$  mg/mg
- Proportion of subjects experiencing a confirmed  $>30\%$  decrease from baseline in eGFR at each timepoint

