## 13.8 Statistical and Analytical Methods

### 13.8.1 Primary Efficacy Analysis

The primary efficacy endpoint is the renal response at Week 52 (Section 13.7.1, [Primary Endpoint](#)).

The study null hypothesis  $H_0$  and alternative hypothesis  $H_1$  are as follows:

$H_0$ : There is no difference in renal response between Orelvo and placebo.

$H_1$ : There is a difference in renal response between Orelvo and placebo.

The null hypothesis  $H_0$  will be rejected in favor of  $H_1$  if there is evidence at the 5% significance level using a 2-sided test.

The primary efficacy analysis will be conducted on the ITT set using logistic regression with terms for treatment, baseline UPCR, biopsy class, and MMF use at baseline. The results being expressed as an odds ratio (and associated two-sided 95% CI) for Orelvo compared to placebo. Odds ratios greater than unity show the odds of response are greater for Orelvo than for placebo and therefore indicate a benefit of the Orelvo treatment arm.

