#### 13.8.3.1 Response Endpoints

The following secondary endpoints will be analyzed using logistic regression as outlined in Section 13.8.1, [Primary Efficacy Analysis](#). These analyses will be conducted on the ITT population and will incorporate baseline variables within the model as appropriate.

- Renal response at Week 52 (based on definition of primary endpoint)

- Partial renal response as defined by 50% reduction from baseline in UPCR at Weeks 24 and 52
- Renal response with low-dose steroids (defined as renal response in the presence of corticosteroids of  $\leq 2.5$  mg between Weeks 16 to 24 and Weeks 44 to 52)

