## **5 RANDOMIZATION**

All subjects enrolled must be identifiable throughout the study. The Investigator will maintain a list of subject numbers and subject names to enable records to be found at a later date. Subjects will be allocated a subject number at the screening visit and registered with an interactive central randomization system. Subjects meeting the required eligibility criteria will be randomized to treatment at Visit 2 (baseline).

The randomization will be stratified by biopsy class (Class V only versus Others) and by prior MMF use at time of screening. The subjects will be randomized in a ratio of 1:1 to receive either voclosporin 23.7 mg BID or matching placebo. To help ensure balance, a centralized randomization will be utilized where region will be employed as a blocking factor. This will ensure balance between treatment groups within each of the 4 regions: North America, Latin America, Europe / South Africa and Asia Pacific.

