#### 6.11.4.2 Proportion of subjects experiencing a confirmed $>30\%$ decrease from baseline in eGFR at each timepoint.

Percent eGFR change for a subject at a given visit will be calculated as:

- $\frac{\text{change from baseline}}{\text{Baseline}} \times 100$

At any two consecutive time points, a subject that achieves a clinically significant  $>30\%$  decrease in eGFR from baseline will be considered a confirmed eGFR drop subject at the earlier timepoint, otherwise they will be considered a non-eGFR drop subject. The proportion of subjects with a confirmed eGFR drop at each visit will be compared using the Chi Square or Fisher exact test if applicable. The proportion of eGFR drop subjects will be summarized at weeks 2, 4, 8, 12, 16, 20, 24, 30, 36, 42, 48 and 52 by treatment group. P-values of the differences at each visit will be reported (Table 14.2.7).

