## 9 CHANGES TO PLANNED PROTOCOL ANALYSIS

In the randomization, regional differences were not expected and blocking by region was done more for drug distribution reasons. While the analysis specified in the protocol stipulated that the regional blocking factor was not to be used in the analysis models, following feedback from regulatory agencies, the models will include terms for each of the factors used in the randomization process:

- Biopsy Class (Class V versus Others)
- MMF use at screening (Yes versus No)
- Region (North America, Latin America, Europe+South Africa and Asia Pacific)

During the regulatory agency review and feedback process it was decided to remove the ‘Duration of UPCR  $\geq 0.5$ ’ endpoint from the list of key-secondary endpoints and place it within the list of ‘Other Secondary Endpoints’. The proportion of subjects experiencing a confirmed  $>30\%$  decrease from baseline in eGFR at each timepoint was also removed from the list of key secondary endpoints. To this end, neither endpoint will form part of the hierarchical testing procedure.

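### The confirmed >30% eGFR-decrease endpoint is compared by an unadjusted test, unlike the SAP's other binary secondary endpoints, and SAP Section 9 does not record the difference

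*SAP*

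**What the plan says.** SAP 6.11.4.2 compares the proportion with a confirmed eGFR decrease of more than 30% at each visit from Week 2 to Week 52, 12 visits in all. The arms "will be compared using the Chi Square or Fisher exact test if applicable". The section adds that "P-values of the differences at each visit will be reported". It names no covariate, stratification factor, effect estimate or confidence interval, and does not say when Fisher's test becomes applicable.

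The protocol synopsis states: "Other binary endpoints will be analyzed in a similar manner to the primary endpoint". In Protocol 13.8.1 the primary analysis is done "using logistic regression with terms for treatment, baseline UPCR, biopsy class, and MMF use at baseline"; SAP 6.11.2.1 adds region.

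The body of the protocol is less explicit. Section 13.8.3.1 begins "The following secondary endpoints will be analyzed using logistic regression as outlined in Section 13.8.1" and lists renal response at Week 52, partial renal response and renal response with low-dose steroids. The eGFR endpoint is a key secondary endpoint in Protocol 13.7.2.1 but is not on that list, and no other part of Section 13 gives it a method.

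On randomisation, SAP Section 5 says "The randomization will be stratified by biopsy class (Class V only versus Others) and by prior MMF use at time of screening", with region as a blocking factor. SAP Section 9 explains that region was added to the models and that the eGFR endpoint and the duration endpoint left the key secondary list, so that "neither endpoint will form part of the hierarchical testing procedure". It does not mention the test chosen for the eGFR endpoint.

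**The concern.** Loss of renal function is a known concern with this drug. Protocol 1.2.5 reports an early eGFR drop of at least 30% in a small proportion of voclosporin-treated subjects in the lupus nephritis experience. It also reports permanent discontinuation for decreased GFR in 1 subject (1.1%) on placebo against 6 (6.7%) on the low dose, which is the dose tested here. SAP 6.11.4.2 is where confirmed loss is compared between arms as a proportion.

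For such an endpoint the reader needs an estimate of the difference and the range of harm still compatible with the data, on the same footing as the other binary results. A run of unadjusted p-values does not give that. The factors that would align the analysis with the randomisation are already collected. Because Section 9 is silent, a reader who relies on it to find departures from the protocol would not see this one.

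**Working it through.** **1. The texts side by side**

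| Binary endpoint | Method in the SAP |
|---|---|
| Renal response, Week 52 (6.11.2.1) | Adjusted logistic regression |
| Partial renal response (6.11.3.2) | As the primary |
| Renal response, Week 24 (6.11.3.4) | Similar to the primary |
| Renal response with low-dose steroids (6.11.4.8) | Similar to the primary |
| Confirmed >30% eGFR decrease (6.11.4.2) | Unadjusted chi-square or Fisher |

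The eGFR endpoint is the exception, and no reason is given.

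**2. The plan's own figure**

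The documents give no event rate or power for this endpoint. The only stated figure is for the primary: 20.0% against 34.4%, two-sided 0.05, 162 per arm, 80% power by a continuity-corrected chi-square test. The formula returns 163 per arm, and power at 162 is 79.9%, so the figure reproduces. I use 162 per arm below, assuming every subject is assessed.

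**3. What stratifying would gain**

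Simulation of 3,000 trials per scenario: N = 324, 2 × 2 × 4 = 16 strata (biopsy class × MMF use × region) and 1:1 allocation within strata. Assumed inputs: placebo event rate 3% to 20%; odds ratio 1 or 2.1; standard deviation of the strata effect 0.5 or 1.0 on the logit scale; strata shares of 15/85 for biopsy class, 45/55 for MMF use and 10/28/28/34 for region. CMH is the stratified Cochran-Mantel-Haenszel test.

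Rejection rates at odds ratio 1: chi-square 3.7% to 4.8%, CMH 4.2% to 5.5%, Fisher 2.3% to 3.5%.

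Power at odds ratio 2.1:

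| Placebo rate | SD | Chi-square | CMH | CMH minus chi-square |
|---|---|---|---|---|
| 3% | 0.5 | 26.3% | 26.5% | +0.2 |
| 3% | 1.0 | 32.3% | 33.8% | +1.5 |
| 5% | 0.5 | 41.6% | 42.2% | +0.6 |
| 5% | 1.0 | 45.6% | 47.9% | +2.3 |
| 10% | 0.5 | 63.3% | 64.3% | +1.0 |
| 10% | 1.0 | 63.7% | 67.4% | +3.7 |
| 20% | 0.5 | 82.3% | 83.3% | +1.0 |
| 20% | 1.0 | 76.3% | 80.4% | +4.1 |

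So the unadjusted tests show no inflation of the type I error. The gain from stratifying is about 0 to 1 point for moderate strata effects and about 1.5 to 4 points for strong ones.

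**4. What the Fisher option costs**

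I enumerated all binomial outcomes at 162 per arm. With equal arms and m events in total, the smallest expected count is m/2. A conventional trigger of an expected count below 5 (my assumption; the SAP states none) therefore means m/2 < 5, or fewer than 10 events in both arms together.

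| Assumed event rates | Chi-square always | Fisher always | Fisher only if expected count < 5 | Trials in which Fisher is used |
|---|---|---|---|---|
| 5% v 12% (power) | 63.0% | 55% | 63.0% | about 0.002% |
| 3% v 8% (power) | 51.1% | 41% | 51.0% | 1.4% |
| 5% v 5% (size) | 4.9% | 2.6% | 4.8% | 3.6% |
| 3% v 3% (size) | 4.5% | 2.0% | 3.3% | 49% |

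Using Fisher throughout would cost 8 to 10 points of power in these examples. Under the conventional trigger the cost is 0.1 point or less. Visible conservatism remains only when events are very few.

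**The case against.** The case for leaving the section alone has four parts.

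- **The protocol rule is thin.** It is one synopsis sentence, and it asks only for a similar manner of analysis. Protocol 13.8.3.1 omits this endpoint from the logistic list. SAP 6.2.12 requires the randomisation factors as covariates in the primary analyses, and Section 9 speaks of models, which a chi-square test is not. This stands in part. A reader might infer that the SAP breaks a firm protocol requirement. The documents support less than that: the synopsis sentence is the only protocol text that covers the endpoint, and the SAP differs from it without saying so.
- **A confidence interval is already required.** SAP 6.11 asks for a 95% interval with every treatment comparison, and 6.11.4.2 also summarises proportions by arm. This stands. A reader might infer from 6.11.4.2 that p-values are all that will be reported, but the general rule says otherwise. What remains is that 6.11.4.2 does not name the measure or the interval.
- **The choice of test is not a route to a favoured result.** A reader might see the switch as analytic flexibility. With equal arms, an expected-count trigger depends on the pooled number of events and not on the treatment difference. This stands on the conventional reading. The fair criticism is that no trigger is written down.
- **Adjustment can fail with few events.** Sixteen strata and few early events can make an adjusted model unstable. This supports an exact fallback. It does not support making the unadjusted test the unexplained default.

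In addition, eGFR is examined in the primary endpoint, in its component analyses (SAP 6.11.2.3) and as change from baseline (SAP 6.11.4.6), so this comparison does not carry the renal assessment alone.

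**Conclusion.** The point holds as a minor inconsistency in method and reporting. SAP 6.11.4.2 uses an unadjusted test where the synopsis and the SAP's other binary secondary endpoints point to the adjusted primary approach. Section 9 does not record the difference, the section omits the interval that SAP 6.11 requires, and the Fisher trigger is undefined.

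No confirmatory claim depends on it, since the endpoint is outside the Hochberg family. Stratifying would gain about 0 to 4 points of power. That range rests entirely on assumed event rates and strata effects, because the documents give none.

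A reader might go further and conclude that Fisher's conservatism will hide a renal harm signal. That would need Fisher to be used throughout, which the wording of 6.11.4.2 does not say. Under the expected-count trigger the loss is 0.1 point or less in the two power examples. Nor do the calculations support a reading that the unadjusted test is invalid. The main benefit of a change is an interpretable estimate with its interval, comparable with the other binary results.

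**What to change.** In SAP 6.11.4.2, report at each visit a Mantel-Haenszel risk difference stratified by biopsy class, MMF use and region, with its 95% confidence interval and a p-value from the corresponding stratified test. State in advance how sparse strata are collapsed.

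Keep an exact test only as a fallback with a written trigger, for example an expected count below 5. Record the method and its reason in Section 9. If the unadjusted test is retained instead, Section 9 should say so and why, and 6.11.4.2 should name the interval that SAP 6.11 requires.

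The cost is SAP wording and minor programming. The one drawback is that a collapsing rule has to be agreed, since with 16 strata some will be nearly empty of events at early visits. No new data are needed.

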#### **6.11.4.3 Change from baseline in UPCR at each time point**

The response variable for the MMRM model will be the change from baseline in serum creatinine. Change from baseline in UPCR will be summarized at weeks 2, 4, 8, 12, 16, 20, 24, 30, 36, 42, 48 and 52 (Table 14.2.8.1). Listings of this endpoint will be provided with lab data. Baseline is calculated as defined in Section 6.2.2.

A supplementary analysis of change from baseline in UPCR will be undertaken using the alternative baseline definition (section 6.2.2) of the lowest UPCR value pre-dosing.

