#### **Change from baseline endpoints**

Change from baseline in UPCR endpoints will be analyzed using a Mixed Effect Model Repeated Measures analysis with treatment arm, visit, treatment by visit interaction, biopsy class, MMF use at baseline, region and baseline UPCR included as a covariates in the model. Results will be expressed as differences between treatment arms (along with the associated 95% CI). The observed and change from baseline values will be summarized by treatment visit and treatment arms. The LS means and their corresponding 95% CI of the change from baseline values will also be presented for each visit and for the overall change. The model will be fitted using an unstructured (UN) covariance matrix. Should the UN covariance matrix not converge, then an autoregressive (AR(1)) covariance matrix will be used. The covariance matrix used will be indicated in the footnotes. The Kenward-Roger degree of freedom adjustment will be applied. LS mean plots of mean change from baseline versus visit will be presented for UPCR and eGFR.

The SAS code anticipated to be used for analysis of the change from baseline endpoints is as follows:

```
Proc Mixed data=dataset;  
Class Treatment biopsy_class MMF_use Region visit subject;  
Model response = Treatment biopsy_class MMF_use Region visit visit*treatment baseline/ DDFM=KR  
Repeated Visit/subject =subject Type= UN R Corr;  
LSmeans visit*treatment/PDIFF CL E;  
Run;
```

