#### **6.11.4.4 Change from baseline in serum creatinine**

Serum creatinine data will be available in lab data. The response variable, change from baseline in serum creatinine, will be summarized at Weeks 2, 4, 8, 12, 16, 20, 24, 30, 36, 42, 48 and 52 (Table 14.2.9). Listings of this endpoint will be provided with lab data. Baseline is calculated as defined in Section 6.2.2

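### SAP 6.11.4.3, the UPCR change-from-baseline section, names serum creatinine as the MMRM response variable and so contradicts the rest of the plan

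*SAP*

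**What the plan says.** SAP 6.11.4.3 is the endpoint-specific section for change from baseline in UPCR, reported in Table 14.2.8.1. It opens: "The response variable for the MMRM model will be the change from baseline in serum creatinine". The next sentence returns to UPCR: "Change from baseline in UPCR will be summarized at weeks 2, 4, 8, 12, 16, 20, 24, 30, 36, 42, 48 and 52". The section ends with a further UPCR analysis: "A supplementary analysis of change from baseline in UPCR will be undertaken using the alternative baseline definition".

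The general method stands earlier in SAP 6.11.4, under the heading on change from baseline endpoints. It begins "Change from baseline in UPCR endpoints will be analyzed using a Mixed Effect Model Repeated Measures analysis" and has "region and baseline UPCR included as a covariates in the model". It also promises graphical output: "LS mean plots of mean change from baseline versus visit will be presented for UPCR and eGFR".

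The section after the UPCR one, SAP 6.11.4.4, deals with serum creatinine and Table 14.2.9: "The response variable, change from baseline in serum creatinine, will be summarized" at the same visits.

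Protocol 13.8.3.3 puts UPCR change from baseline at each visit first in its list of endpoints for the MMRM. Serum creatinine is a separate item in that list.

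**The concern.** The sentence is not silent or vague. It states a dependent variable, and that variable belongs to a different endpoint.

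The structure of SAP 6.11.4 makes this more than a slip in background text. The general section supplies one block of SAS code in which the outcome is a placeholder called `response` and the baseline term is a placeholder called `baseline`. Endpoint subsections then say what goes in. SAP 6.11.4.10 does this for SELENA-SLEDAI by naming the change in total score as the response in the MMRM, and SAP 6.11.4.4 to 6.11.4.6 each name their own response variable. The first sentence of 6.11.4.3 is the matching assignment for UPCR, and it assigns creatinine.

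At stake is the correctness of one table. UPCR is a component of the primary endpoint and underlies the key secondary endpoints, so readers will look to its repeated-measures comparison as supporting evidence. That comparison should not rest on instructions that disagree with each other.

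**Working it through.** No arithmetic applies: the point depends on no sample size, error rate or effect size. The check is to set the relevant texts side by side and ask which response variable each one implies for Table 14.2.8.1.

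| Place | Implied response variable |
|---|---|
| SAP 3.2.2, list of other secondary endpoints | UPCR |
| SAP 6.11.4, general change-from-baseline text | UPCR, with baseline UPCR as covariate and LS mean plots for UPCR |
| SAP 6.11.4.3, heading | UPCR |
| SAP 6.11.4.3, first sentence | **Serum creatinine** |
| SAP 6.11.4.3, by-visit summaries (Weeks 2 to 52, 12 visits) | UPCR |
| SAP 6.11.4.3, supplementary analysis with the lowest pre-dose baseline | UPCR |
| Protocol 13.8.3.3, MMRM list | UPCR |

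One entry out of seven disagrees with the others.

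1. **Is it a deliberate change?** SAP section 9 records departures from the protocol analysis: adding region to the models and moving two endpoints out of the key secondary list. It says nothing about replacing or dropping the UPCR repeated-measures model.

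2. **Is creatinine otherwise uncovered, so that the sentence fills a gap?** No. SAP 6.11.4.4 gives it its own section and Table 14.2.9.

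3. **What would literal execution produce?** Table 14.2.8.1 would hold a model of change in creatinine. Taken with the general text, that model would be adjusted for baseline UPCR. Creatinine would then be the named response for two tables, 14.2.8.1 and 14.2.9. The supplementary analysis in 6.11.4.3, which is explicitly on UPCR, would supplement a main model of a different variable. No reading of the plan suggests that this was intended.

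4. **Does the wrong name leave the scale of the UPCR analysis open?** No. SAP 6.11.3.2 defines UPCR change as the post-baseline value minus the baseline value and defines percent change separately, for the 50% reduction endpoints. SAP 6.2.2 fixes the UPCR baseline as the mean of the latest 2 pre-randomization values and gives the alternative baseline.

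5. **How far does it reach?** SAP 6.11.5 applies the Hochberg procedure to five key secondary comparisons: time to UPCR at or below 0.5 mg/mg, partial renal response at Week 52 and at Week 24, time to 50% reduction in UPCR, and renal response at Week 24. UPCR change from baseline is not among them.

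**The case against.** The strongest reply is that nobody could be misled. The heading, the rest of the section, the general MMRM text and the protocol all point to UPCR, creatinine is handled next door, and the endpoint carries no controlled error rate. On this view the sentence is a copying slip that any competent programmer would query.

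Much of that stands, and it rules out three stronger readings that a reader might draw from the sentence alone:

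- **That the UPCR repeated-measures analysis would not be run.** The general text in SAP 6.11.4 and Protocol 13.8.3.3 both specify it, and 6.11.4.3 itself plans UPCR summaries and a supplementary UPCR analysis.
- **That this is the only place where the response variable is fixed in advance.** The same two texts fix it as well.
- **That the sponsor could choose raw, percent or log change after seeing the data.** The definition in SAP 6.11.3.2 points to the absolute difference, and no log transform is mentioned for this endpoint.

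What the reply does not remove is the contradiction. The sentence is operative specification text for a named table, and it is wrong as written. That the right answer can be worked out from elsewhere lowers the consequence but does not make the instruction correct.

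**Conclusion.** The point holds as an internal contradiction in the analysis specification. SAP 6.11.4.3 names the wrong MMRM response variable, against its own heading and remaining text, the general MMRM section and the protocol. The intended analysis is recoverable. The practical risk is a wrong dependent variable in Table 14.2.8.1 if the endpoint-specific sentence is followed alone.

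The size is small: one other-secondary endpoint, with no effect on the primary analysis or on the key secondary tests.

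The conclusion rests on two assumptions. The first is that UPCR is the intended variable, which every other relevant statement supports. The second is that programmers take the response variable from the endpoint subsections, as the placeholder code suggests. The list of tables in SAP section 11 has no entries in the text available here, so whether the title of Table 14.2.8.1 would itself flag the error could not be checked.

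**What to change.** In the first sentence of SAP 6.11.4.3, replace serum creatinine with UPCR. A cross-reference to SAP 6.11.3.2 for the definition of change (post-baseline minus baseline) would be useful but adds no new rule.

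Confirm that the shell and program for Table 14.2.8.1 use UPCR as the response and baseline UPCR as the covariate.

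The cost is a one-word text correction, with no new data, no added analysis and no change to sample size or error control. It is best made before database lock. After lock, the discrepancy and its resolution should be noted in the clinical study report, where Protocol 13.1 already requires deviations from the SAP to be explained.
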